***Modifying the final phase of the study based on findings from interim analyses***

Interim analyses of the pre-Month 6 study data have provided new information related to some of the study’s main research questions and have informed modifications to the final phase of the study. Consistent with observations in HIV-negative populations, mRNA-1273 appears safe and well tolerated in PLWH. Reactions after vaccinations were largely mild, with few severe reactions (3%) and no life-threatening or fatal reactions. To date, adverse events in general have been overwhelmingly mild and only one serious adverse event (a case of angioedema) has been considered potentially related to the vaccine. The pre-Month 6 data also suggest that in our study population, participants with hybrid immunity (ie, immunity from both prior infection and vaccination) experienced a reduced incidence of symptomatic SARS-CoV-2 infections compared to participants with only vaccine-induced immunity. Specifically, PLWH and HIV-negative participants who had evidence of prior SARS-CoV-2 infection at baseline and received one dose of mRNA-1273 had an annual COVID-19 incidence rate of 2.2% and 1.5% respectively, compared to 7.1% and 5.8% among such groups without evidence of prior infection at baseline and received two doses of mRNA-1273. This reduction in SARS-CoV-2 incidence could be due to the combination of natural immunity and mRNA-1273 vaccination or due to natural immunity alone. In addition, serious COVID-19 has been very rare in our study population during the pre-Month 6 period, with only 9 cases identified to date, including 7 in PLWH and 2 in people who were HIV-negative. However, asymptomatic SARS-CoV-2 infections were more common than previously appreciated, representing 86% of pre-Month 6 cases. In addition, the data suggest that there are a significant number of likely persistent infections. Of the 1298 (9.3%) participants with at least

one SARS-CoV-2 positive NAAT, 5.6%, 1.8%, and 1.5% were persistently NAAT positive at  $\geq 25$ , 50, 100 days, respectively. Deep genome sequencing of the sequential samples will help determine if these are persistent infections or reinfections (likely both) and what proportion of infections have acquired mutations. The persistent/recurrent infections appear to be more common among the participants without prior SARS-CoV-2 infection, those with active tuberculosis, and PLWH who have low CD4 T-cell counts and/or HIV viremia.

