The Ubuntu study enrolled a total of 14,237 participants into 4 study groups based on their baseline HIV serostatus (positive or negative) and anti-spoke SARS-CoV-2 Point-of-Care serology (POCS) status (positive or negative). Prior to protocol version 6.0, for Part A of the study, participants were assigned to receive 1 dose (Month 0), or 2 doses (Month 0 and Month 1) of mRNA-1273 based on their baseline POCS result being positive or negative, respectively. Prior to protocol version 6.0, for Part B of the study, randomization code was generated but all participants received the monovalent mRNA-1273 vaccine at Month 6 due to the bivalent vaccine not being available at the time, and no randomization assignment was actually performed. At the time of implementation of protocol version 6.0 after the bivalent vaccine became available, The Ubuntu study enrolled a total of 14,237 participants into 4 study groups based on their baseline HIV serostatus (positive or negative) and anti-spoke SARS-CoV-2 Point-of-Care serology (POCS) status (positive or negative). Prior to protocol version 6.0, for Part A of the study, participants were assigned to receive 1 dose (Month 0), or 2 doses (Month 0 and Month 1) of mRNA-1273 based on their baseline POCS result being positive or negative, respectively. Prior to protocol version 6.0, for Part B of the study, randomization code was generated but all participants received the monovalent mRNA-1273 vaccine at Month 6 due to the bivalent vaccine not being available at the time, and no randomization assignment was actually performed. At the time of implementation of protocol version 6.0 after the bivalent mRNA-1273.222 vaccine became available, the previous randomization code was replaced with the randomization code generated under an updated randomization plan, ensuring that the treatment number assigned at original “randomization” was kept and corresponded to either mRNA-1273 or mRNA-1273.222. This allowed the site to use the randomized assignment to define the Month 6 vaccination for participants receiving the Month 6 vaccination under protocol version 6.0. An updated treatment key was provided to sites with participants who re-consented on protocol version 6.0, for documenting the Month 6 vaccinations only. Only as many treatment assignments as

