For all primary and secondary comparisons and a subset of exploratory analyses, the time origin for time-to-event COVID-19 or severe COVID-19 endpoints is either the day of or 13 days after the Month 6 vaccination visit, counting events either starting 1 day or 14 days after the Month 6 vaccination. For a subset of exploratory analyses that will include information from enrollment until Month 12 or Month 18, the time origin is either the date of enrollment or 13 days after the Month 6 vaccination visit, counting events either starting 1 day after enrolment or 14 days after the Month 6 vaccination. The Cox model approach will always use the calendar time scale and the cumulative incidence approach will always use the study time scale. See more details about these two approaches in later sections. These analyses will address the co-primary objectives, key secondary objectives and exploratory objectives specified in the protocol (Version 8.0).

Different analyses specify different time origins for the COVID-19 or severe COVID-19 (if applicable) time-to-event T ; the endpoint date is always the same: the date of the first occurrence of COVID-19 or severe COVID-19 endpoint after the corresponding time-origin and up to the date of Month 12 or Month 18 visit. The failure time T is right-censored by the first event of receipt

of outside vaccination, loss to follow-up, or reaching the upper window of the Month 12 (for the Month 12 analyses) or Month 18 visit (for the final analyses), whichever occurs first.

5 SARS-CoV-2 status at baseline and at Month 6

This section defines baseline and Month 6 SARS-CoV-2 statuses, as well as recent SARS-CoV-2 infection status at Month 6 for the pre- & post-M6 stage combined analyses and for the post-M6 stage analyses. These variables will be used as a stratification variable to define different analysis groups, evaluated as a covariate to adjust for prior exposure, and/or as a potential effect modifier in various analyses.

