Baseline SARS-CoV-2 status is defined in the same way as in the Pre-Month 6 stage SAP. Specifically, in addition to the Point-of-Care serology (POCS) testing result, which was used for assigning participants into the 4 study groups at enrolment, the central lab serology (CLS) testing result and the Nucleic Acid Amplification Test (NAAT) result are also used to define the SARS-CoV-2 naïve and non-naïve status in subsequent statistical analyses. Specifically, a participant is said to be baseline SARS-CoV-2 naïve (or negative) if all 3 test are negative. A participant is said to be non-naïve (or positive) if at least 1 of the 3 tests is positive. We will further differentiate between two types of non-naïve participants: (i) those who tested negative for POCS but positive for either CLS or NAAT; and (ii) those who tested positive for POCS. These definitions will be applied after imputing missing baseline CLS and NAAT testing results according to the following imputation scheme. For participants who missed the CLS result but had both POCS and NAAT results, the missing CLS result was imputed as positive if either POCS or NAAT was positive and negative if both POCS and NAAT were negative. For participants who missed the NAAT result but had both POCS and CLS results, the missing NAAT result was always imputed as negative. For participants who missed both CLS and NAAT test results, their missing CLS test result was imputed as positive if POCS result was positive and negative if the POCS result was negative. Their NAAT result was always imputed as negative. This imputation scheme was motivated by the joint distribution of POCS, CLS and NAAT among those who had complete measurements of test results (more than 98% of the study cohort); see Table 1 for various empirical conditional probabilities. We also considered these conditional probabilities separately in the stratum defined by baseline HIV status; results were qualitatively similar and the derived imputation scheme was the same.

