Month 6 SARS-CoV-2 status, a new variable for Part B analyses, is defined as hybrid immunity or vaccine immunity. Specifically, a participant is said to have Month 6 hybrid immunity if they have any evidence of prior SARS-CoV-2 infection up to the Month 6 visit as defined by meeting any of the following criteria: 1) baseline overall SARS-CoV-2 status is positive as defined above, 2) at least one NAAT result at or prior to Month 6 is positive, or 3) at least one CLS at or prior to Month 6 is positive. Otherwise, a participant is said to have Month 6 vaccine immunity. In another word, a participant is considered having only vaccine immunity at Month 6 if absent of any evidence of SARS-CoV-2 infection from enrollment up to Month 6. Of note, POCS results are expected to be available from all participants only for their M0 samples; CLS results are expected to be available from all participants for both their M0 and M6 samples.

Lastly, recent SARS-CoV-2 infection status at Month 6, another new variable for Part B analyses,

Table 1: **Panel A:** Empirical probability that CLS or NAAT test result was positive conditional on different configurations of the other two test results among 13,857/14,040 participants with all three test results measured at baseline. **Panel B:** Empirical probability that CLS or NAAT was positive conditional on POCS test result among 13,929/14,040 participants with both CLS and POCS test results and among 13,915/14,040 participants with both NAAT and POCS test results, respectively.

	Value
Panel A	
$P(\text{CLS} = 1 \text{POCS} = 0 \ \& \ \text{NAAT} = 0)$	0.29
$P(\text{CLS} = 1 \text{POCS} = 1 \ \& \ \text{NAAT} = 0)$	0.58
$P(\text{CLS} = 1 \text{POCS} = 1 \ \& \ \text{NAAT} = 1)$	0.80
$P(\text{CLS} = 1 \text{POCS} = 0 \ \& \ \text{NAAT} = 1)$	0.59
$P(\text{NAAT} = 1 \text{POCS} = 0 \ \& \ \text{CLS} = 0)$	0
$P(\text{NAAT} = 1 \text{POCS} = 1 \ \& \ \text{CLS} = 1)$	0.07
$P(\text{NAAT} = 1 \text{POCS} = 1 \ \& \ \text{CLS} = 0)$	0
$P(\text{NAAT} = 1 \text{POCS} = 0 \ \& \ \text{CLS} = 1)$	0.23
Panel B	
$P(\text{CLS} = 1 \text{POCS} = 0)$	0.32
$P(\text{CLS} = 1 \text{POCS} = 1)$	0.59
$P(\text{NAAT} = 1 \text{POCS} = 0)$	0.07
$P(\text{NAAT} = 1 \text{POCS} = 1)$	0.04

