Calendar-time-based Cox proportional hazards models will be employed to estimate the hazard ratio (HR) between the bivalent vs. monovalent randomized arms. The model will be stratified by the 4 study groups and region (RSA vs. other), thus allowing for a different baseline hazard for each of the $4 \times 2 = 8$ strata. Since the comparison is between randomized groups, the main analysis will only adjust for a small number of covariates that are deemed important or known to be associated with COVID-19 risk to increase efficiency in statistical inference. In particular, sex-assigned-at-birth (Female vs. Male) and baseline history of TB (yes vs. no) were found associated with CDC endpoints in Part A analyses, and having had a recent infection is expected to be associated with COVID-19 risk. Therefore, sex-assigned-at-birth, history of TB at Month 6, and recent SARS-CoV-2 infection status at Month 6 (see definition in Section 5) will be adjusted for in all primary and secondary analyses comparing randomized bivalent vs. monovalent boost arms. These analyses will also be repeated within people who live with HIV (PLWH) and HIV-negative participants, separately. For analyses among PLWH, CD4 counts (\leq vs. > 500 cells/mm 3 at Month 6) and HIV viral load (detectable vs. not detectable at Month 6) will be further adjusted for in

addition to sex assigned at birth, history of TB and recent infection status. For analyses among HIV-negative participants, a subset of the covariates maybe considered to avoid data sparsity, with recent SARS-CoV-2 status as the leading covariate to consider. Specifically, for Cox regression among HIV-negative participants (PLWoH), we will not adjust for TB status due to data sparsity.

We also make comparisons of covariate-adjusted cumulative incidence curves for each comparison arm. We provide a full description of the covariate-adjustment strategies in Section 11.3.

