7.2 Exploratory analyses comparing bivalent and monovalent boost arms

For post-M6 follow-up in Part B of the study, exploratory comparisons of COVID-19 and severe COVID-19 risk between the bivalent and monovalent boost arms will consider the Full Month 6 cohort (FM6) and count events starting 14 days after the Month 6 vaccination. Because these comparisons are not between randomized arms, covariate-adjusted study-group-and-region stratified Cox models and covariate-adjusted cumulative incidence analysis approaches will be employed. The same list of covariates described above for the primary and secondary analyses will be considered. Exploratory analyses will be performed inferentially using the cumulative incidence approach, but covariate adjustment will only be made in the presence of enough failure events (because of the stability issue of the resulting estimator); details can be found in Section 11.3.

The same exploratory analyses will be repeated within people living with HIV (PLWH) and HIV-negative participants, separately.

8 Parts A+B analyses: Pre- & post-M6 stage combined

All described analyses below will start counting events after study enrolment or 13 days after the Month 6 vaccination, based on follow-up till the Month 12 visit and the Month 18 visit. Again, the Cox model approach will always use the calendar time scale and the cumulative incidence approach will always use the study time scale. These analyses will not adjust for multiple looks of the data.

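### In the non-randomised exploratory analyses I–II, the covariate set cannot tell previously infected from naive participants among those who were point-of-care seronegative

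*SAP*

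**What the plan says.** SAP Section 5 sets out baseline SARS-CoV-2 status, Month 6 status and recent infection status together. It says they may define analysis groups or be "evaluated as a covariate to adjust for prior exposure, and/or as a potential effect modifier in various analyses".

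- **Baseline status** combines POCS, CLS and NAAT: "A participant is said to be non-naïve (or positive) if at least 1 of the 3 tests is positive". The section separates out a subtype (i), negative on POCS but positive on CLS or NAAT.
- **Month 6 status**: "Month 6 SARS-CoV-2 status, a new variable for Part B analyses, is defined as hybrid immunity or vaccine immunity". Hybrid means "any evidence of prior SARS-CoV-2 infection up to the Month 6 visit", which includes a positive baseline status.
- **Recent infection status** covers only new infection during Part A.

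The four study groups, by contrast, were formed from HIV serostatus and POCS alone (SAP Section 2).

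For the randomised comparison, SAP Section 7.1 stratifies the Cox model by study group and region. It adjusts for sex and TB history, and "recent SARS-CoV-2 infection status at Month 6 (see definition in Section 5) will be adjusted for in all primary and secondary analyses". CD4 count and viral load are added in people living with HIV (PLWH). The cumulative-incidence models use recent infection and study group (Section 11.3.1).

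Section 7.2 then turns to the full Month 6 cohort (FM6), where the SAP itself says the arms were not formed by randomisation: "The same list of covariates described above for the primary and secondary analyses will be considered". Sections 8.2.1, 11.3.2 and 11.4.3 carry the same sets into exploratory analyses I–II. Month 6 hybrid/vaccine status is used only in Section 8.2.2, to define a group for exploratory analyses VI–VII.

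**The concern.** In a non-randomised comparison the covariates have to do the work of randomisation, and prior infection is an obvious candidate confounder. Study-group stratification captures it for POCS-positive participants. It does not capture it for those who were POCS-negative but CLS- or NAAT-positive. Such a person with no new Part A infection shares a stratum (given region) and a recent-infection value with a naive person, so the model cannot separate them.

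There is a reason why the arms could differ. Before version 6 every Month 6 dose was monovalent, and bivalent doses were given only under version 6 (SAP Section 2). The study began in December 2021 (Protocol Section 2.1.3) and version 6.0 is dated 27 September 2022 (Protocol Section 13). Month 6 is Day 169. The added monovalent recipients therefore generally enrolled earlier in the epidemic than the bivalent recipients. A calendar-time Cox model deals with a hazard that changes over time, but not with different infection histories among people at risk on the same date. The cumulative-incidence approach uses study time and lacks even that protection.

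At stake is residual confounding in two exploratory estimates of bivalent versus monovalent effect.

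**Working it through.** **1. Share of POCS-negative participants who are not naive.** Inputs from SAP Table 1: P(CLS+ | POCS−, NAAT−) = 0.29; P(CLS+ | POCS−, NAAT+) = 0.59; P(NAAT+ | POCS−) = 0.07; stated P(CLS+ | POCS−) = 0.32.

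- Reproducing the stated figure: 0.29 × 0.93 + 0.59 × 0.07 = 0.311. Rounding of the inputs gives 0.305 to 0.318, so 0.32 is met at the rounding edge.
- CLS or NAAT positive: 1 − (1 − 0.07) × (1 − 0.29) = 0.34 (rounding range 0.33 to 0.35).

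Two printed cells do not fit the others. The 0.59 implies P(NAAT+ | POCS−, CLS−) = 0.41 × 0.07 / 0.68 = 0.04, but 0 is printed. It also implies P(NAAT+ | POCS−, CLS+) = 0.59 × 0.07 / 0.32 = 0.13, but 0.23 is printed. Neither of those two printed cells is used above. CLS alone gives 0.32 and CLS or NAAT gives 0.34, so about a third holds.

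**2. What the recent-infection term recovers.** Criterion 2 in Section 5 needs a negative baseline anti-N result, and criterion 3 is not used at Month 12. In the Month 12 analyses a participant who was anti-N positive at baseline can therefore be flagged only by a new positive NAAT.

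**3. Illustrative bias within Groups 1 and 3.** Let p0 and p1 be the non-naive shares in the monovalent and bivalent arms, and r the rate ratio for prior infection.

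Shift = [1 − p1(1 − r)] / [1 − p0(1 − r)]

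Assumptions: p0 = 0.34; r from 0.31 to 0.7. The lower value comes from Protocol Section 2.1, where PLWH and HIV-negative participants with prior infection "had an annual COVID-19 incidence rate of 2.2% and 1.5% respectively, compared to 7.1% and 5.8"% without it; for PLWH, 2.2/7.1 = 0.31. The value 0.7 is a weaker effect chosen to show the range.

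| r | p1 − p0 | Calculation | Shift |
|---|---|---|---|
| 0.31 | +10 points | 0.696 / 0.765 | 0.91 |
| 0.31 | −10 points | 0.834 / 0.765 | 1.09 |
| 0.7 | +10 points | 0.868 / 0.898 | 0.97 |
| 0.7 | −10 points | 0.928 / 0.898 | 1.03 |
| either | 0 | – | 1.00 |

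At r = 0.31 a 20-point imbalance gives 0.82 or 1.18.

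**4. Pooled over four groups.** Assume the 1:2 ceiling sizes of Protocol Table 1-1 and a relative rate of r in the POCS-positive groups. At r = 0.31, Groups 1 and 3 supply 0.765 / (0.765 + 2 × 0.31) = 0.55 of events. Weighting the log shift by events, the pooled value for +10 points is about 0.91^0.55 = 0.95. At r = 0.7 the share is 0.898 / (0.898 + 1.4) = 0.39 and the pooled value is about 0.97^0.39 = 0.99.

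**The case against.** The strongest reply is that little of consequence is at risk and the size is conjecture.

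- **Two secondary outputs.** Exploratory I–II are labelled non-randomised, and Section 8.2 warns that not all of the exploratory analyses there may be done for the primary publication. This stands, and limits the point to a cheap improvement.
- **The inputs are borrowed.** The 0.31 compares one-dose hybrid with two-dose vaccine-only participants before Month 6. The people in question were assigned two doses and are followed after a further one. No document gives a non-naive share by booster arm. This also stands: the figures show sensitivity only.
- **No commitment is broken.** A reader might infer that Section 5 promised adjustment for Month 6 status. It does not. Adjustment is one of several uses joined by and/or, and the variable is used as a group definition in Section 8.2.2.
- **Month 6 status overlaps terms already present.** It is constant in Groups 2 and 4, and in Groups 1 and 3 it is hybrid for everyone with a recent infection. That favours baseline three-test status as the term to add. It does not make Month 6 status useless: among people without a Part A infection, the two separate the same participants.

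None of this answers the structural gap: the listed covariates cannot distinguish the two kinds of POCS-negative participant.

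**Conclusion.** The gap is real and confined to exploratory analyses I–II. About a third of POCS-negative participants (0.32 to 0.34) are non-naive by the SAP's own rule, yet are modelled as naive unless they had a new Part A infection. That share refers to the enrolled cohort with test results, not to FM6.

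Whether this biases the comparison depends on an arm imbalance that is plausible from the timing of dosing but not documented. Size and direction are unknown. Under the stated assumptions a 10-point imbalance moves the ratio by 3% to 9% within Groups 1 and 3, and by about 1% to 5% pooled.

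Three stronger readings are not supported:

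- That the primary and secondary results are biased. Those arms were randomised within study group, so the omission there can cost only precision.
- That the omission favours the bivalent vaccine. The sign could be either.
- That prior infection is the strongest known predictor. The protocol's interim rates show a marked difference but rank no predictors, and the groups compared also differ in number of doses.

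**What to change.** For exploratory analyses I–II only:

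1. Add baseline three-test status, that is, an indicator for subtype (i) of Section 5 (POCS-negative but CLS- or NAAT-positive), to the Cox models in Sections 7.2, 8.2.1 and 11.4.3. Add it also to the outcome, censoring and propensity models used under Section 11.3.2. Month 6 hybrid/vaccine status entered alongside recent infection would serve nearly as well.
2. Tabulate that status by booster arm in FM6, so that readers can see whether any imbalance exists.
3. If the term is left out, say why.

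Cost: one binary variable that Section 5 already defines, which fits the binary-covariate restriction in Section 11.3.2. If the Section 7.1 rule of five endpoints per covariate carries over, the threshold rises by five events. With all participants it goes from 15 to 20 (three covariates to four), which equals the existing 20-endpoint minimum. In PLWH it goes from 25 to 30. The randomised primary and secondary analyses stay as they are.

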6.1 Co-Primary COVID-19 endpoint

According to Version 8 of the protocol, all symptomatic COVID-19 endpoints will be evaluated using two case definitions, one used in the COVE study and the other using a case definition based on criteria from the CDC, with the latter being the leading definition given the lighter-symptom

nature of omicron infections observed and anticipated from the study. No multiplicity adjustments are applied to adjust for analyses of multiple COVID-19 endpoints.

